### 220 **2.3 Participant Exclusion Criteria**

221 Individuals meeting any of the following exclusion criteria at baseline will be excluded from  
222 study participation.

223 1. Prior use of Tandem t:slim X2 insulin pump with Control-IQ technology  
224 2. Two or more episodes of severe hypoglycemia (needing assistance) in the past 6 months  
225 3. History of inpatient psychiatric treatment in the past 6 months  
226 4. History of drug abuse (defined as any illicit drug use) or history of alcohol abuse prior to  
227 screening or unwillingness to agree to abstain from illicit drugs throughout the study.  
228 5. History of significant heart disease, lung disease, liver disease, chronic kidney disease, or  
229 other systemic disease determined by investigator to interfere with the study, or make  
230 required exercise unsafe  
231 6. History of significant vision, hearing, or dexterity problems that will impair use of the  
232 closed loop system  
233 7. Use of glucocorticoids, beta blockers, sulfonylureas, meglitinides or other medications  
234 specifically listed in section 8.3 of the protocol or determined by investigator to interfere  
235 with the study  
236 8. Unstable dose of SGLT-2 inhibitor, GLP-1 receptor agonist, or other adjuvant medication  
237 specifically listed in section 8.3 of the protocol, or starting a new glucose lowering agent  
238 during the trial.  
239 9. Unstable dose of any medication used for weight loss, as listed in section 8.3 of the  
240 protocol, or starting a new medication for weight loss during the trial.

241 10. Abnormal screening electrocardiogram consistent with increased risk during exercise,  
242 such as arrhythmia, ischemia, or prolonged QTc interval (>450 ms)  
243 11. History of hemodialysis  
244 12. History of adrenal insufficiency  
245 13. Uncontrolled hypo- or hyperthyroidism  
246 14. Significant diabetes related complications, based on investigator assessment  
247 15. Immediate family member (spouse, biological or legal guardian, child, sibling, parent)  
248 who is an investigative site personnel directly affiliated with this study or who is an  
249 employee of Tandem Diabetes Care, Inc.

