### 1096                   **8.3 Prohibited Medications, Devices, Treatments, and Procedures**

1097 Participants using other insulins at the time of enrollment will be asked to contact their personal  
1098 physician to change their prescribed personal insulin to lispro or aspart for the duration of the  
1099 trial.

1100 AfreZZa (inhaled insulin) or concurrent use of basal insulins will not be permitted during device  
1101 use in the trial. Additional medications to treat glycemia (such as SGL-2 inhibitors or GLP-1  
1102 receptor agonists), commonly used by individuals with type 2 diabetes concurrently with insulin  
1103 use, will be allowed if the participant is on a stable dose of such medication for the last 3 months.  
1104 Sulfonylurea use and meglitinide use will not be allowed during the trial.

1105 No new additional glucose lowering medications may be added during the trial.

1106 Medications used for weight loss will be allowed if the participant is on a stable dose of such  
1107 medication for the last 3 months. No new medications for weight loss may be added during the  
1108 trial.

1109 Additional medications may be excluded per judgement of the investigator.

1110 The investigational study devices (study insulin pump, study CGM system) must be removed  
1111 before Magnetic Resonance Imaging (MRI), Computed Tomography (CT) or diathermy treatment.  
1112 Participants may continue in the trial after temporarily discontinuing use if requiring one of the  
1113 treatments above.

1114                   **8.4 Precautionary Medications, Treatments, and Procedures**

1115   Not applicable.

1116                   **8.5 Prophylactic Medications, Treatments, and Procedures**

1117   Not applicable.

1118                   **8.6 Rescue Medications, Treatments, and Procedures**

1119   All participants will be required to have a commercially available glucagon (or glucagon analog)  
1120   preparation for treatment as needed of severe hypoglycemia.

1121                   **8.7 Pregnancy Reporting**

1122   If pregnancy occurs, the participant will be discontinued from the study. The occurrence of  
1123   pregnancy will be reported to the Coordinating Center within seven days and to the JCHR IRB as  
1124   an Unanticipated Problem within seven calendar days.

1125                   **8.8 Participant Compensation**

1126   Participant compensation will be specified in the informed consent form.

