#### 4.3 Calculation of Overall CGM Metrics (primary and secondary):

- One Week of Baseline: The last 7 days of personal CGM data before enrollment or last 7 days of CGM run-in data will serve as baseline. If a participant has <24hr of data in the last 7 days of CGM personal or run-in and if more CGM data are available beyond the 7 days, then will go backwards 24hr at one time until the minimum of 24hr of CGM data are reached. At least 24hr of data during baseline are required for the glycemic metrics to be calculated. These are Dexcom sensor data.
- Six Weeks of CLC use: All CGM data following the midnight of the initiation of CLC use visit day and the midnight right before the end of study visit day will be included irrespective if the system was in closed-loop mode or not. Since the exercise sessions are designed as challenges to the system and the data to be analyzed for safety events, the CGM data between the start of the exercise and 6:00AM next morning will be analyzed separately (see Section 8.1 below) and not included here. On the other hand, since the meals are not designed to be challenges to the system, the CGM data following the meals will be included here even if also analyzed separately (see

Section 8.1 below). If the end of 6 weeks of CLC use visit is more than 6 weeks away from the CLC use initiation visit for a participant, then the CGM data will be truncated at 6 weeks (i.e., 42 days). At least 168hr of data during these 6 weeks of CLC use are required for the glycemic metrics to be calculated and for a participant to be included in the primary and secondary analyses. These are Tandem pump CGM data and will include data following meals and during exercise periods.

- Two-four Weeks of Open Loop (OL) use: All CGM data between the initiation of Open-Loop use and the start of CLC will be used. At least 24hr of data during this period are required for the glycemic metrics to be calculated. These are Tandem pump CGM data.
- All CGM metrics during baseline, OL, and CLC periods will be calculated giving equal weight to each sensor reading for each participant.

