## 4.6 Calculation of Insulin Metrics

184     • Will include only days with complete insulin data and at least 7 such days are required for the  
185       metrics to be calculated. If there are not such 7 days, the participants will not be included in the  
186       insulin analyses. Since Tandem pump automatically generates a basal record every hour, at least  
187       20 such hourly records are required for a day to be considered complete with insulin data and to  
188       be counted towards the minimum of 7 days.  
189     • Will be calculated only during the 6 weeks of CLC use and are based on the Tandem pump  
190       insulin delivery data.  
191     • As with the CGM metrics, if a participant stayed in the study more than 6 weeks, then the insulin  
192       data will be truncated at 6 weeks from the initiation of CLC use.  
193     • Weight at baseline will be used to calculate units/kg metrics.

194  
195  
196 **4.7. Questionnaires**

197 Participants are allowed to skip specific questionnaires or items within a questionnaire. The data might  
198 therefore include some missing items. If applicable, questionnaires will be scored according to the  
199 instructions given in the manual. If a total or a sub-scale score is calculated but no instructions exist,  
200 then at least 75% of the items should be non-missing for the total or sub-scale score to be calculated.

201  
202 **4.8 Analysis Windows**

203 Analysis windows apply to the following outcomes measured at 6-week final visit:

204     • Weight  
205     • Questionnaires

206 To be included in the corresponding analyses, these data must be collected between days 28 and 56 from  
207 the beginning of CLC period. The target date is 42 days from the beginning of CLC period.

208 This does not apply to the CGM and insulin metrics which are calculated as described above.

211  
212 **5. Description of Statistical Methods**

213     **5.1. General Approach:**

214     • Since this is not a randomized trial, the intention-to-treat (ITT) principle does not apply.  
215     • In the unlikely event that an enrolled participant is later found to be ineligible, the participant  
216       will be excluded from all analyses.  
217     • Otherwise, all enrolled participants with at least 168h of CGM data during the 6-week of CLC  
218       use will be included in the primary and secondary analyses.  

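### Exclusion criteria 8 and 9 count drugs started after baseline, and SAP 5.1 does not limit its removal of ineligible participants to facts at enrollment, so membership of the primary and safety sets is not fixed

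*Protocol*

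**What the plan says.** Protocol 2.3 opens its list with "Individuals meeting any of the following exclusion criteria at baseline will be excluded from" the study. Criterion 8 then names unstable adjuvant medication "specifically listed in section 8.3 of the protocol, or starting a new glucose lowering agent" in the course of the trial. Criterion 9 ends in the same way: "protocol, or starting a new medication for weight loss during the trial". The Protocol Summary and the SAP's Table 1 repeat both criteria without the sentence that fixes the time point.

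Protocol 8.3 states the same matter as a prohibition: "No new additional glucose lowering medications may be added during the trial". It has a parallel sentence for weight-loss drugs. It gives no consequence for the analysis, and protocol 7.6.1 does not name a new drug among the reasons for discontinuing a participant.

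SAP 5.1 sets the analysis rule: "In the unlikely event that an enrolled participant is later found to be ineligible, the participant" "will be excluded from all analyses". The next bullet begins "Otherwise, all enrolled participants with at least 168h of CGM data during the 6-week of CLC" and places those participants in the primary and secondary analyses. SAP 5.2 and SAP 8 say that the safety analyses include all participants.

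**The concern.** Nobody can meet a clause about a later drug start at baseline. Because these clauses sit in the exclusion list, someone who starts a drug in week 3 of closed loop meets a listed criterion. Nothing in SAP 5.1 confines ineligibility to facts true at enrollment. One statistician could drop this person and another could keep them, and the choice could be made after the data are seen.

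Two things are at stake. First, the primary comparison is a single-arm paired change, so removing people for an event after baseline can select on response. Second, removal from every analysis contradicts the all-participants safety set. That second conflict arises for any participant found ineligible, not only for someone who starts a drug.

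**Working it through.** **No planned figure to reproduce.** Protocol 9.3 and SAP 3 describe 30 participants, with at least 24 completing, as a convenience sample. They give no SD, effect size or power.

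**The passages side by side**

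| Place | Time limit on a drug start | Consequence for analysis |
|---|---|---|
| Protocol 2.3, lead-in | Baseline only | Not excluded on this reading |
| Protocol 2.3, criteria 8 and 9 | While the trial runs | Listed as an exclusion |
| SAP Table 1, criteria 8 and 9 | While the trial runs; no baseline lead-in | Listed as an exclusion |
| Protocol 8.3 | While the trial runs | Prohibited; no analysis consequence |
| SAP 5.1 | None stated | If ineligible, out of all analyses |
| SAP 4.3 | None stated | Closed-loop CGM used whether or not the loop was active; no cut at a new drug |
| SAP 5.2, per-protocol | None stated | Depends only on closed-loop use of at least 80% |
| SAP 5.2 and 8, safety | None stated | All participants included |

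No row settles which reading governs the primary set, and the SAP 5.1 and safety rows disagree.

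**Size of the removal effect on mean change in % >180.** Let n be the number before removal, k the number removed, and g the number of points by which their mean change is worse than that of the rest. Dropping them shifts the mean by −k × g / n. The values of k and g are assumptions.

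- n = 24, k = 1, g = 10: −10/24 = −0.42 points.
- n = 24, k = 1, g = 20: −20/24 = −0.83 points.
- n = 30, k = 1, g = 10 to 20: −10/30 = −0.33 to −20/30 = −0.67 points.
- Direct check of the 20-point case at n = 24: if 23 participants average −10 and one has +10, the mean is (23 × (−10) + 10)/24 = −9.17. Without that one it is −10.0, a shift of −0.83.

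If g is zero the shift is zero. If those removed were doing better than the rest, the shift goes against the device.

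**Effect on the test.** The planned two-sided 0.05 paired t-test was simulated with no true device effect (40,000 runs, normal differences, assumed SD 10, 15 or 20). The nominal chance of a significant result in the device's favour is 0.025. Removing exactly the 1, 2 or 3 worst responders raised it to about 0.067, 0.129 and 0.213 at n = 30, and 0.070, 0.140 and 0.235 at n = 24 (both SD 15). The other SDs gave nearly the same values. These figures are extreme, because they assume that the people removed are precisely the worst responders.

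**Scale of the safety conflict.** If 30 participants each complete 42 days, exposure is 30 × 42/365 = 3.45 person-years. One event is then 100/3.45 = 29 per 100 person-years in the rates planned in SAP 8. Dropping one person who had an event would remove that amount from the reported rate.

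**The case against.** The strongest reply is that removal is a strained reading. The lead-in to protocol 2.3 governs the whole list and limits it to baseline. A rule about someone later found ineligible ordinarily concerns late discovery of an old failure, not a later event. The clauses in criteria 8 and 9 may simply restate the prohibition in 8.3. New drugs are barred, closed loop lasts six weeks, and poor control is to be met by adjusting insulin settings, so cases should be few. Medications are recorded (protocol 8.2), and starting a barred drug would be a protocol deviation, which is tabulated (protocol 9.10, SAP 10).

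Most of this stands. It makes removal one reading among others and cases rare. It does not settle the matter, because the SAP's own copy of the criteria lacks the baseline limit. The protocol also applies eligibility after enrollment: enrollment occurs at consent (2.1.1), and people who fail eligibility at the run-in reviews are withdrawn (3.4, 3.8). There is a third route as well. If the participant withdraws, protocol 8.9 keeps the data up to that point, but no text requires withdrawal for a new drug.

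A reader might infer that the plan favours the device either way: by dropping poor responders, or by keeping them and crediting the drug to closed loop. The documents do not support that. They do not say why a drug would be started, and a weight-loss drug need not signal poor glucose control. Keeping a participant does include any glucose-lowering effect of the drug, because nothing in the SAP separates it. But keeping everyone is a defensible primary analysis and the one recommended here, so that route supports at most an optional extra table.

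**Conclusion.** The point holds as an ambiguity about who is analysed, plus a direct contradiction over the safety set. It does not show that the plan removes such participants, nor that the primary result is biased towards the device. The direction after removal depends on an unstated assumption, that those removed were doing worse than the rest. The size is small: about 0.4 to 0.8 points of mean change in % >180 per case at n = 24, for an assumed gap of 10 to 20 points. The number of cases, the gap and the SD are all absent from the documents. The change is still worth making, because it fixes set membership before the data are seen, costs almost nothing, and the results are meant to inform a larger study.

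**What to change.** Reconcile protocol 2.3, protocol 8.3 and SAP 5.1 so that they describe a drug started after enrollment in the same way. No co-medication rule needs to change. In SAP 5.1, state that:

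- the ineligibility exclusion covers only criteria failed on facts true at enrollment, including those established by the screening tests;
- it never removes a participant from the safety analyses;
- participants who start a glucose-lowering or weight-loss drug after enrollment stay in the primary analysis, subject to the existing 168-hour CGM requirement, and the start is recorded as a protocol deviation.

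Optionally, report how many participants had a new or dose-changed drug of these kinds, from the medication data in protocol 8.2. Add one sensitivity analysis of both primary outcomes using closed-loop CGM before that date. This cut has a weakness that should be reported with it. The SAP baseline precedes the 2 to 4 weeks of open loop, so a drug started in open loop leaves no usable closed-loop data, and a start in the first week of closed loop leaves less than 168 hours. State how many participants are lost in each way.

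The cost is one wording change and, if the option is taken, one extra table.

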## 250 **2.4 Screening Procedures**

251 After informed consent has been signed, a potential participant will be evaluated for study  
252 eligibility through the elicitation of a medical history, performance of a physical examination by  
253 study personnel and local laboratory testing if needed to screen for exclusionary medical  
254 conditions.

255 The screening visit must be completed within 28 days of participant enrollment.

### 256 **2.4.1 Data Collection and Testing**

257 A standard physical exam (including vital signs and height and weight measurements) will be  
258 performed by the study investigator or designee (a physician, fellow, nurse practitioner or a  
259 physician assistant).

260 The following procedures will be performed/data collected/eligibility criteria checked and  
261 documented:

- 262 • Inclusion and exclusion criteria assessed
- 263 • Demographics (date of birth, sex, race and ethnicity)
- 264 • Contact information (retained at the site and not entered into study database)
- 265 • Medical history, including existing comorbidities deemed clinically relevant (e.g.  
266 retinopathy, nephropathy, neuropathy, history of cardiovascular events); in addition, details  
267 specific to type 2 diabetes, including age at diagnosis, duration of disease, previous therapy,  
268 and frequency of severe hypoglycemia will be collected
- 269 • Concomitant medications
- 270 • Physical examination to include:
  - 271 ◆ Weight, height
  - 272 ◆ Vital signs including measurement of blood pressure and pulse
- 273 • An electrocardiogram (ECG) will be administered and read locally by the investigator to  
274 determine if the participant meets eligibility criteria with respect to the exercise component  
275 of the study
- 276 • Fingerstick or blood draw for point-of-care or local laboratory determination of baseline  
277 HbA1c level and any local laboratory testing required for eligibility assessment

278 • Blood draw for Central Lab determination of HbA1c and C-peptide with concurrent glucose  
279 level

280 • Urine or serum pregnancy test for all women who have reached menarche and are  
281 premenopausal and are not surgically sterile

282     • Barrier methods, oral contraceptives, and implantable and/or IUD-type contraceptives are  
283         examples of methods that constitute acceptable methods of contraception for females of  
284         child-bearing potential, and will be discussed with all such females who are not  
285         postmenopausal or surgically sterile.

286     • Females are considered premenopausal per investigator discretion, typically with less  
287         than 1 year since last menses.

288 • Participants will complete a set of baseline questionnaires, described in section 6.3

289 Screening procedures will last approximately 1-2 hours.

290 **2.5 Screen Failures**

291 Individuals who do not initially meet study eligibility requirements may be rescreened once at a  
292 later date per investigator discretion.

293

294

## 295                   **Chapter 3: CGM and Pump Run-in Phases**

### 296                   **3.1 CGM Run-in Phase Overview**

297                   This phase must begin within 7 days of completion of the Screening visit. The purpose of this  
298                   CGM run-in phase is to 1) assess compliance with study procedures and 2) to introduce the study  
299                   CGM to study participants without current use of a Dexcom CGM.

300                   Participants who currently use a Dexcom G6 CGM with at least 85% of possible CGM readings  
301                   captured during the 14 days prior to enrollment can skip the CGM Run-in phase. Participants who  
302                   do not currently use a Dexcom G6 CGM, or who do use that CGM but have <85% of possible  
303                   CGM readings in the 14 days prior to the time of enrollment, will be required to participate in the  
304                   CGM Run-in phase.

305                   Participants will receive training on the study CGM as detailed below. This will be an unblinded  
306                   use of the study CGM.

### 307                   **3.2 Initiation of CGM**

308                   During an in-clinic visit that may coincide with the Screening visit, study CGM supplies will be  
309                   provided and the participant will be instructed to use the study CGM on a daily basis. Participants  
310                   using a personal CGM prior to the study will discontinue the personal CGM beginning in this  
311                   period.

#### 312                   **3.2.1 CGM Training**

313                   CGM training will be provided by a qualified trainer to participants not currently using a personal  
314                   CGM identical to the study CGM as to how to use it in real-time to make management decisions  
315                   and how to review the data after an upload for retrospective review. CGM training will include:

- 316                   • Instruction on how to insert the sensor and transmitter, including observation/supervision  
317                   of placement of a sensor
- 318                   • Instruction on how to calibrate the CGM unit, if needed
- 319                   • Guidance on accessing the CGM trace, either through a manufacturer-provided software  
320                   app or via a study-provided CGM receiver unit, or via a personal insulin pump if  
321                   participants use a pump that integrates with the study CGM
- 322                   • Participants will be asked to perform fingerstick blood glucose measurements in  
323                   accordance with the labeling of the study CGM device

324                   A copy of the study CGM user's guide will be provided to the participant.

325                   Participants may use available manufacturer-provided CGM software and features of the study  
326                   CGM related to mobile data access or remote monitoring, but will be instructed not to use any  
327                   third-party components for this purpose. The t:connect mobile app from Tandem Diabetes Care  
328                   will not be available for use during the trial, and will not pair to the study pump.

329                   Upon completion of the CGM training components, study staff will document, using a checklist,  
330                   that the participant is familiar with the functions/features/tasks addressed during the training.

331                   **3.3 Blood Glucose and Blood Ketone Testing**

332           Participants will receive supplies for blood glucose and blood ketone testing.

333           • Blood glucose testing

334            ○ Participants will be provided with a study blood glucose meter, test strips, and any  
335            software/hardware needed to download meter data .

336            ○ All study blood glucose meters will be QC tested with control solution if available prior to  
337            dispensation. *A tested meter will not be used in a study if it does not read within the target*  
338            *range at each concentration per manufacturer labeling.*

339            ○ Participants will be reminded to use the study blood glucose meter for all fingerstick BGs  
340            during the study.

341            ○ Participants will be given guidelines for treatment of low or high blood glucose.

342           • Blood ketone testing

343            ○ Participants will be provided with a study blood glucose meter, test strips, and any  
344            software/hardware needed to download meter data.

345            ○ All study blood ketone meters will be QC tested with control solution if available prior to  
346            dispensation. *A tested meter will not be used in a study if it does not read within the target*  
347            *range at each concentration per manufacturer labeling.*

348            ○ Participants will be reminded to use the study blood ketone meters per the study  
349            hyperglycemia safety plan

350            ○ Participants will be given guidelines for treatment of positive ketone readings.

351           • Participants will be required to have glucagon at home. Participants who currently do not have  
352           one will be given a prescription for glucagon as part of standard care (either emergency kit for  
353           injections or nasal glucagon per investigator discretion).

354                   **3.4 Assessment of Successful Completion of the CGM Run-in Phase**

355           Enrolled participants will have a follow-up visit approximately 14 days after initiation of the run-  
356           in phase to assess progress or successful completion of the phase. If needed, one or more interim  
357           visits or phone contacts may occur to assist the participant with any CGM use issues. Procedures  
358           will include downloading of the study CGM data and the following:

359           • Assessment of compliance with the use of CGM to obtain at least 85% of possible CGM  
360           valued during the run-in period

361           • Assessment of skin reaction in areas where a CGM sensor was worn or other safety issues  
362           associated with CGM use

363           • Assessment of eligibility to continue to the pump run-in phase of the study

364           Participants who fail to meet the minimum CGM use requirement, or who the investigator believes  
365           may benefit from an extension of the CGM run-in period, may at the investigator's discretion be  
366           allowed to continue CGM run-in for a second ~2-week period. These participants will have another  
367           follow-up visit approximately 14 days after the prior visit for a reassessment using the same  
368           procedures as described above.

369 Participants who do not meet CGM use requirements after two 2-week periods of CGM run-in or  
370 otherwise fail to meet study eligibility requirements will be withdrawn from the study.

